6.2.8. Incidence of SAEs and AEs leading to discontinuations

The incidence of SAEs and AEs leading to discontinuation will be summarized by treatment group using the safety analysis set.

6.2.9. Proportion of participants with COVID-19-related hospitalization >24 hours, or death from any cause through Day 28

The proportion of participants with COVID-19-related hospitalization >24 hours, or death from any cause through Day 28 will be summarized. The cumulative proportion of participants hospitalized for the treatment of COVID-19 or death during the first 28 days of the study will be estimated for each treatment group using the Kaplan-Meier method to take account of losses to follow-up and summarized graphically for each treatment group.

For participants without an event who complete the Day 28 assessment, they will be censored at Day 28. For participants without an event who discontinue or are lost to follow-up before the Day 28 assessment, they will be censored at the last known date in the study.

6.2.10. Proportion of participants with death (all cause) through Week 24

The proportion of participants who died from any cause through Week 24 will be analyzed using the method specified in Section 6.2.9 and summarized for each treatment group. KM plots for each treatment group will also be provided. Participants without an event will be censored at the last known date in the study.

6.2.11. Proportion of participants with COVID-19-related hospitalization of any duration

The proportion of participants with COVID-19-related hospitalization of any duration will be analyzed using the method specified in Section 6.2.9 and summarized by treatment arm

DMB02-GSOP-RF02 7.0 Statistical Analysis Plan Template 31-Jan-2022 PFIZER CONFIDENTIAL TMF Doc ID: 98.03 Page 20 of 32 through day 44 and through week 24. Participants without an event (at Day 44/Week 24) will be censored at that time or at the last known date in the study, whichever is later.

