6.2.16. Duration of each targeted COVID-19 signs/symptoms

Duration of each targeted COVID -19 signs/symptoms is defined as (First Date when the symptom alleviated/resolved) – (First Dose Date) +1 for each participant with baseline severity of mild, moderate, or severe.

For a participant that either completes the Day 44 visit of the study or discontinues from the study before the Day 44 visit without alleviation/resolution of signs/symptoms (censored), censoring date will be at the date of discontinuation from the study or day 44 whichever comes first, and time will be calculated as (Censoring Date) – (First Dose Date) +1.

Symptoms Alleviation through day 44 of each targeted COVID-19 sign/symptom is defined as **the first time** when each targeted symptom scored as moderate or severe at study entry are scored as mild or absent AND a targeted symptom scored mild or absent at study entry are scored as absent.

Symptoms Resolution through day 44 of each targeted COVID-19 sign/symptom is defined as the first time when each targeted symptom scored as mild, moderate or severe at study entry are scored as absent.

DMB02-GSOP-RF02 7.0 Statistical Analysis Plan Template 31-Jan-2022 PFIZER CONFIDENTIAL TMF Doc ID: 98.03 Page 21 of 32 For symptoms with no reported severity in baseline, the symptom will have to be absent in order to be counted as alleviated/resolved (missing severity at baseline will be treated as mild).

For duration of each targeted COVID19 sign/symptom, a Kaplan-Meier analysis providing the event rate, median and quartiles will be provided for each treatment arm.

6.2.17. Proportion of participants with severe signs/symptoms attributed to COVID-19 through Day 44

Participants will record a daily severity rating of their symptom severity over the past 24 hours based on a 4-point scale in which 0 is reported if no symptoms were present; 1 if mild; 2 if moderate; and 3 if severe.

Vomiting and diarrhea will each be rated on a 4-point frequency scale where 0 is reported for no occurrence, 1 for 1 to 2 times, 2 for 3 to 4 times, and 3 for 5 or greater. Sense of smell and sense of taste will each be rated on a 3-point Likert scale where 0 is reported if the sense of smell/taste was the same as usual, 1 if the sense of smell/taste was less than usual, and 2 for no sense of smell/taste.

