Rebound in SARS- CoV-2 RNA up to Day 28 (NP) defined as a half \log_{10} copies/mL increase or greater relative to EOT (active) with follow-up viral RNA level \geq 3.0 \log_{10} copies/mL	Secondary	Evaluable with EOT (active) and 1 post-EOT not missing	No imputation for missing data	Descriptive (n, %)
Proportion with COVID-19-related hospitalization >24 hours, or death through Day 28	Secondary	Evaluable	Max censor time at Day 28	KM method
Proportion with death (all cause) through Week 24	Secondary	FAS	Max censor time at Week 24	KM method
Proportion with COVID-19-related hospitalization	Secondary	Evaluable	Max censor time at Day 44	KM method
Proportion with COVID-19-related ICU admission	Secondary	Evaluable	Max censor time at Day 44	KM method
Proportion requiring IMV or ECMO	Secondary	Evaluable	Max censor time at Day 44	KM method
Number of days in hospital and ICU stay	Secondary	Evaluable, participants with COVID- 19-related hospitalizat ion	In the absence of a specific record of a COVID-19-related hospitalization, participants will be considered to be out of hospital	Descriptive summary

DMB02-GSOP-RF02 7.0 Statistical Analysis Plan Template 31-Jan-2022 PFIZER CONFIDENTIAL TMF Doc ID: 98.03 Page 28 of 32

Endpoint	Analysis Type	Population	Data Inclusion and Rules for Handling Intercurrent Events and Missing Data	Analysis Model
Number of COVID- 19-related medical visits through Day 44 and through Week 24	Secondary	Evaluable	In the absence of a specific record of a COVID-19-related medical visit, participants will be considered to not have a COVID- 19-related medical visit.	Descriptive summary
Duration of each targeted COVID-19 signs/symptoms	Secondary	Evaluable	No imputation for missing data	KM method
Proportion with severe signs/symptoms attributed to COVID-19	Secondary	Evaluable	No imputation for missing data	Descriptive (n, %)

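### SAP 6.2.11–6.2.13 censor at the later of the horizon and the last known date, so participants lost early count as event-free and the rates of hospitalization, ICU admission and ventilation/ECMO are understated

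*SAP*

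**What the plan says.** SAP 6.2.11 (hospitalization of any duration), 6.2.12 (ICU admission) and 6.2.13 (invasive mechanical ventilation or ECMO) share one construction. Each adopts the method of 6.2.9 and reports results "through day 44 and through week 24". Each then adds that participants without an event "will be censored at that time or at the last known date in the study, whichever is later".

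Other parts of the SAP treat follow-up differently:

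- **6.2.9** (hospitalization over 24 hours or death, Day 28) estimates the cumulative proportion "using the Kaplan-Meier method to take account of losses to follow-up". Event-free participants who "discontinue or are lost to follow-up before the Day 28 assessment, they will be censored at the last known date in the study".
- **6.2.10** (all-cause death, Week 24): "Participants without an event will be censored at the last known date in the study".
- **6.2.16** (symptom duration): the "censoring date will be at the date of discontinuation from the study or day 44 whichever comes first".
- **Appendix 1** gives the three endpoints at issue "Max censor time at Day 44". It has no Week 24 entry for them.

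**The concern.** Censoring should remove a participant from the risk set when observation stops. Taking the later of two dates does the opposite for anyone who leaves early: the participant is carried as observed and event-free over weeks in which nobody saw them. Protocol 7.2 and 7.3 make such losses possible, since no further data are collected after consent for future information is withdrawn and unreachable participants count as withdrawn.

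The rule also puts the censoring time of a participant followed to Week 24 at Week 24 in the Day 44 analysis, against the Appendix 1 cap.

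Three secondary endpoints on severe outcomes would be biased downward by a prespecified rule. If losses differ between arms, the bias differs too, and any reading across durations is distorted.

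**Working it through.** **Inputs.** The rules are those set out above. About 50 participants per arm in the main population comes from SAP 2.4. The Week 24 target is Day 168 (SAP Appendix 2.1). The documents state no event rate, dropout rate or precision for these endpoints, so there is no figure of the plan's own to reproduce. All event times and losses below are assumptions.

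**Step 1: the two rules.** Let T be the horizon (44 or 168) and L the last known date of an event-free participant.

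- As written in 6.2.11–6.2.13: C = max(T, L). With L = 7, C = 44 at the first horizon and 168 at the second.
- As in 6.2.9: C = min(T, L). With L = 7, C = 7 at both.

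Applying the Appendix 1 cap to the written rule gives min(max(T, L), T) = T for everyone, so the cap does not repair it.

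**Step 2: consequence.** The estimate is 1 − Π(1 − dᵢ/nᵢ) over event times. Under the written rule nobody leaves before T except through an event, so the product telescopes to (N − D)/N and the estimate is D/N, the crude proportion. Under the 6.2.9 rule each nᵢ is the same or smaller, so the estimate is the same or larger. The two agree only if nobody is lost early or every event precedes every loss.

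**Step 3: worked cases, N = 50.**

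| Assumed case | As written | Censored as in 6.2.9 |
|---|---|---|
| Day 44, 3 events, 5 lost before the first | 3/50 = 6.0% | 3/45 = 6.7% |
| Day 44, 3 events, 10 lost before the first | 6.0% | 3/40 = 7.5% |
| Day 44, events on Days 6, 12, 20, 30; 5 lost on Day 10 | 4/50 = 8.0% | 1 − (49/50)(41/44) = 8.68% |
| Same events, 10 lost on Day 10 | 8.0% | 1 − (49/50)(36/39) = 9.54% |
| Day 44, 4 events all before the losses | 8.0% | 8.0% |
| Week 24, 2 events before and 2 after Day 44; 8 lost at Day 44 | 8.0% | 1 − (48/50)(38/40) = 8.8% |
| Same, 12 lost at Day 44 | 8.0% | 1 − (48/50)(34/36) = 9.3% |

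The first two rows are understatements of 10% (6.0/6.67 = 0.90) and 20% (6.0/7.5 = 0.80) in relative terms.

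**Step 4: losses and events spread evenly.** With constant hazards, true risk p and dropout q by the horizon, put λ = −ln(1 − p) and γ = −ln(1 − q). The written rule has expectation λ/(λ + γ) × [1 − e^−(λ+γ)]. For p = 10%:

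- q = 5%: 9.75%
- q = 10%: 9.50%
- q = 20%: 8.98%
- q = 30%: 8.44%

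For p between 2% and 20%, the ratio to the true risk is about 0.975, 0.95, 0.90 and 0.84–0.85 at these four dropout levels. Simulation with n = 50 and 4,000 runs per scenario agreed. At 10% risk and 20% dropout, the means were 10.13% (earlier date) and 9.09% (later date), and in no run of any scenario did the later-date estimate exceed the other.

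**Step 5: across arms.** Two arms with the same true 10% risk but 5% and 20% dropout would be expected to show 9.75% and 8.98%, an artificial gap of 0.77 percentage points.

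**The case against.** The best case on the other side is that the SAP states conflicting rules, not one wrong rule. Each section first points to 6.2.9, which handles losses properly. A maximum censor time in Appendix 1 makes sense only if censoring can fall earlier. The sentence might also be read as covering only participants still under observation at the horizon. All this supports a slip in wording. It does not remove the problem: the specific sentence is repeated three times, and a programmer would normally follow it over a general cross-reference.

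It could instead be deliberate. For days in hospital and medical visits, Appendix 1 treats no record as no event. But that convention would conflict with the stated reason for using Kaplan-Meier, "Kaplan-Meier method to take account of losses to follow-up".

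Several qualifications stand:

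- Placing every loss before the first event is the worst ordering. Even spreading roughly halves the relative bias for the same losses, and the Week 24 figures depend on the two-and-two split. With three events before and one after Day 44, they become 8.4% and 8.7%.
- The Day 44 gap of 0.7 to 1.5 points is small beside a 95% half-width of 1.96 × √(0.06 × 0.94/50) ≈ 6.6 points. It is systematic, however, and avoidable.
- Censoring after Day 44 in the Day 44 analysis contradicts Appendix 1 but cannot change the Day 44 estimate. Only early losses cause bias.
- No formal between-arm comparison is planned for these endpoints, so only informal comparison is affected.
- Death without the event is a competing event. Censoring at death makes one minus Kaplan-Meier overstate cumulative incidence, so the earlier-date rule matches 6.2.9 without being free of every bias.
- Stopping study drug is not withdrawal (Protocol 7.1), which limits losses.

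**Conclusion.** The concern holds. Taken literally, the rule in SAP 6.2.11, 6.2.12 and 6.2.13 is wrong, reverses the method those sections cite, and differs from 6.2.10 and 6.2.16. The downward direction is certain whenever a participant is lost before a later event. The size is conditional on loss and event timing that the documents do not give: from nothing, through about 5% and 10% relative at 10% and 20% dropout under constant hazards, to 10% and 20% relative if the same losses all precede the events. Week 24 is probably worse, since more loss can accumulate. The primary endpoint, the Day 28 composite and mortality do not use this wording. It should be corrected, but it does not threaten the trial's main result.

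**What to change.** In SAP 6.2.11, 6.2.12 and 6.2.13, change later to earlier, so that an event-free participant is censored at the horizon or the last known date, whichever comes first. In Appendix 1, set the maximum censor time for the three matching rows to Day 44 and Week 24, one for each reported time point.

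The cost is one word in three sections and three table entries, with no new data and no design change. It would help to add a sentence on how death without the event is handled, since these endpoints, unlike the composite in 6.2.9, do not include it.

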6.2.12. Proportion of participants with COVID-19-related ICU admission of any duration

The proportion of participants with COVID-19-related ICU admission of any duration will be analyzed using the method specified in Section 6.2.9 and summarized by treatment arm through day 44 and through week 24. Participants without an event (at Day 44/Week 24) will be censored at that time or at the last known date in the study, whichever is later.

6.2.13. Proportion of participants requiring invasive mechanical ventilation or ECMO

The proportion of participants requiring invasive mechanical ventilation or ECMO will be analyzed using the method specified in Section 6.2.9 and summarized by treatment arm through day 44 and through week 24. Participants without an event (at Day 44/Week 24) will be censored at that time or at the last known date in the study, whichever is later.

6.2.14. Number of days in hospital and ICU stay in participants with COVID-19-related hospitalization

The number of days of hospital stay and number of days of ICU stay in participants with COVID-19-related hospitalization will be summarized through Day 44 and through Week 24 by treatment group using descriptive statistics (ie, mean, median, range).

6.2.15. Number of COVID-19-related medical visits through Day 44 and through Week 24

The number of COVID-19-related medical visits through Day 44 and through Week 24 will be summarized by treatment group using descriptive statistics (ie, mean, median, range).

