**Table 1. Study Schedule of Assessment**

Visit Identifier' Abbreviations used in this table may be found in Section 10.11.	Screening	Baseline (Day 1)	Day 5	Day 10	Day 15	Day 21	Day 28	Day 35	Day 44	LTF/U		ET (pilot to Day 44)	Notes
										Week 12	Week 24		
Visit Window	Day -1 to Day 1	0 days	bl:1 day	bl:1 day	±2 days	±2 days	±2 days	±3 days	±3 days	±1 days	±7 days	±5 days	
 
Screening procedures may be done from Day -1 to Day 1, and may be completed on the same calendar day as Baseline/Day 1 procedures. If screening and baseline visits are conducted on the same calendar day, assessments and procedures that are listed to occur at both visits only need to be completed once.
 

Study intervention accountability			X	X	X							X [if needed]	
 
Study intervention accountability is only performed at the Day 21 visit if the participant administered treatment after the Day 15 visit was conducted.
 

Patient Reported Outcomes													Only adult participants (≥18 years of age) will be asked to complete PRO assessments. 
 
See Section 8.2.4.
 

Collection of global impression questions		X	X	X	X	X	X	X	X	X	X	X	
 
Participants will answer 3 global impression questions.
 
See Section 8.2.4.1.
 

SF-36		X		X		X			X	X	X		
 
See Section 8.2.4.2.
 

WPAI			X		X					X	X		
 
See Section 8.2.4.3.
 

EQ-5D-5L		X	X		X				X	X	X		
 
See Section 8.2.4.4.
 

Study Procedures & Assessments													
Provide participants with study emergency contact card	X												
 
See Section 10.1.11.
 

Collect/update secondary contacts		X	X	X	X	X	X		X	X			
 
See Section 8.1.1.3.
 

Record oxygen support details	X	X	X	X	X	X	X	X	X			X	
 
See Section 8.2.3.
 

Study kit dispensed and participant instructed on its use		X											
 
See Section 8.1.1.2.
 

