### **8.2.2. COVID-19-Related Hospitalizations and Medical Details**

Details of participants' COVID-19-related medical visits (ie, hospitalization of any duration, urgent care, emergency room  $\leq 24$ h) will be collected during study visits, including level of care (ICU status) and dates of utilization, including admission and discharge, as applicable.

Hospitalization  $>24$  hours is defined as  $>24$ h of acute care in a hospital or similar acute care facility, including Emergency Rooms or temporary facilities instituted to address medical needs of those with severe COVID-19. This includes specialized acute medical care unit within an assisted living facility or nursing home. This does not include hospitalization for the purposes of public health and/or clinical trial execution.

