### **8.2.3. Oxygen Support Details**

Type of oxygen support (eg, oxygen supplementation received, mechanical ventilation or ECMO received in hospital) will be collected.

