#### **8.4.1. Time Period and Frequency for Collecting AE and SAE Information**

The time period for actively eliciting and collecting AEs and SAEs (“active collection period”) for each participant begins from the time the participant provides informed consent, which is obtained before undergoing any study-related procedure and/or receiving study intervention, through and including a minimum of 28 calendar days, except as indicated below, after the last administration of the study intervention.

Follow-up by the investigator continues throughout the active collection period and until the AE or SAE or its sequelae resolve or stabilize at a level acceptable to the investigator.

When a clinically important AE remains ongoing at the end of the active collection period, follow-up by the investigator continues until the AE or SAE or its sequelae resolve or stabilize at a level acceptable to the investigator and Pfizer concurs with that assessment.

For participants who are screen failures, the active collection period ends when screen failure status is determined.

If the participant withdraws from the study and also withdraws consent for the collection of future information, the active collection period ends when consent is withdrawn.

If a participant permanently discontinues or temporarily discontinues study intervention because of an AE or SAE, the AE or SAE must be recorded on the CRF and the SAE reported using the PSSA.

After the defined active collection period for safety events, long-term follow-up visits are also conducted at Weeks 12 and 24. Any new SAE occurring during this long-term follow-up period and determined to be related to study intervention must be reported to Pfizer Safety immediately upon awareness and under no circumstance should this exceed 24 hours.

Investigators are not obligated to actively seek information on AEs or SAEs after the participant has concluded study participation. However, if the investigator learns of any SAE,

including a death, at any time after a participant has completed the study, and they consider the event to be reasonably related to the study intervention, the investigator must promptly report the SAE to Pfizer using the PSSA.

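### The SAP plans a Week 24 proportion for mechanical ventilation or ECMO, but oxygen support is scheduled for collection only to Day 44, and SAP Appendix 1 stops the same endpoint at Day 44

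*SAP*

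**What the plan says.** **Analysis.** SAP 6.2.13 refers to the method of SAP 6.2.9, which estimates a cumulative proportion "using the Kaplan-Meier method to take account of losses to follow-up". It sets two horizons, Day 44 and Week 24: the result is to be "summarized by treatment arm through day 44 and through week 24. Participants without an event (at Day 44/Week 24) will be censored". The censoring rule in full is that participants without an event "will be censored at that time or at the last known date in the study, whichever is later".

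**Appendix 1.** The row for invasive ventilation or ECMO in the SAP's summary of efficacy analyses also names Kaplan-Meier, but allows no censoring time beyond Day 44.

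**Source of the data.** Protocol 8.2.3 states: "Type of oxygen support (eg, oxygen supplementation received, mechanical ventilation or ECMO received in hospital) will be collected". In Table 1 of the Schedule of Activities, the row "Record oxygen support details" is marked at Screening, Baseline, Days 5, 10, 15, 21, 28, 35 and 44, and at the early-termination visit, which by its column heading falls before Day 44. Weeks 12 and 24 are blank.

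**Other records after Day 44.** COVID-19-related medical visits are recorded at Weeks 12 and 24. Protocol 8.2.2 describes that record as "including level of care (ICU status) and dates of utilization, including admission and discharge, as applicable"; it does not name ventilation or ECMO. Adjunctive therapeutic procedures stop at Day 44 or early termination. On safety reporting, Protocol 8.4.1 says: "Any new SAE occurring during this long-term follow-up period and determined to be related to study intervention must be reported".

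**Protocol endpoint.** Protocol 9.3.3 lists this endpoint with no time horizon.

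**The concern.** A Kaplan-Meier proportion at Week 24 tells the reader that event-free participants were under observation for the event until Week 24. Here the item that records the event is last scheduled at Day 44, while the censoring rule keeps event-free participants in the risk set to at least Week 24. Time with no scheduled ascertainment is therefore counted as event-free follow-up.

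The study rationale is that immunocompromised patients may progress to severe illness because infection is prolonged. A curve that is flat from Day 44 to Week 24 could be read as evidence that late respiratory failure did not occur, when it shows mainly that nobody was scheduled to ask. Separately, a programmer cannot follow both 6.2.13 and Appendix 1.

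**Working it through.** **1. Length of the gap.** SAP Appendix 2.1 gives target days of 44 and 168 for the two visits. 24 × 7 = 168 reproduces the stated Week 24 day.

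- Nominal gap: 168 − 44 = 124 days; 124/168 = 74% of the horizon.
- Protocol visit windows (Day 44 ± 3, Week 24 ± 7): shortest 161 − 47 = 114 days, longest 175 − 41 = 134 days.
- SAP analysis windows (Day 40 to 49, Day 161 to 175): shortest 161 − 49 = 112 days, longest 175 − 40 = 135 days.

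**2. Is the blank genuine?** The oxygen-support row fills all 12 visit columns: nine marks, two blanks, one mark. The medical-visits row of the same table does carry marks at Weeks 12 and 24. The blanks are therefore unlikely to be an extraction fault.

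**3. Effect on the estimate if 6.2.13 is followed.** The documents give no event rate for this endpoint, so what follows is an illustration. Assume n = 50 in an arm, close to the planned size, with a events recorded by Day 44 and none recorded later. Every event-free participant stays at risk to Day 168, so the estimate is a/50 at both horizons:

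| Events recorded by Day 44 | Day 44 | Week 24 |
|---|---|---|
| 0 | 0% | 0% |
| 1 | 2% | 2% |
| 2 | 4% | 4% |

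**4. What collection to Week 24 would show.** Assume one event on Day 10, five participants lost on Day 20, and b true events after Day 44. The number at risk after Day 44 is 50 − 1 − 5 = 44, and the estimate is 1 − (49/50) × (44 − b)/44.

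| True late events, b | Collected to Week 24 | 6.2.13 with no later capture |
|---|---|---|
| 0 | 2.0% | 2.0% |
| 1 | 4.2% | 2.0% |
| 2 | 6.5% | 2.0% |
| 3 | 8.7% | 2.0% |

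The direction is certain: a late event that is not captured lowers the estimate. The size depends on b, which the documents do not allow anyone to estimate.

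**5. A related fault in the same sentence.** Taking the later of the horizon and the last known date also keeps participants lost before Day 44 at risk to the horizon, against the purpose stated in 6.2.9. If five of 50 are lost by Day 20 and one event occurs on Day 30, the later-of rule gives 1/50 = 2.0%, while censoring at loss gives 1/45 = 2.2%. The effect is small and again in the direction of understatement.

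**6. If Appendix 1 governs.** With a Day 44 cap there is no Week 24 curve, and the unobserved span falls from 124 days to 0.

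**The case against.** The strongest reply has four parts.

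**Some late cases could be found.** A reader might infer that no event after Day 44 can be recorded and that every late case is lost. The documents do not go that far. Protocol 8.2.3 speaks of ventilation received in hospital, and COVID-19-related admissions with ICU status are still asked about at Weeks 12 and 24. The list in 8.2.2 is not worded as exhaustive, and the CRF is not available here. Protocol 8.4.1 and 8.4.3 also require clinically important adverse events still open at the end of active collection to be followed until they resolve or stabilize, so a participant already seriously ill at Day 44 and ventilated later might be captured. This stands, and it limits the claim to the absence of scheduled capture. It does not rescue the Week 24 figure: ICU status is not ventilation, follow-up of ongoing events does not reach new late events, and incidental capture cannot support a proportion.

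**Appendix 1 may govern.** Then no unobserved days are counted. This also stands: the certain defect is the conflict, and the 124 days follow only if 6.2.13 prevails. Appendix 1 puts the same Day 44 cap on hospitalization and ICU admission, against Week 24 text in SAP 6.2.11 and 6.2.12. Those two also need reconciling, but their data are collected at Weeks 12 and 24.

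**Late severe disease would show elsewhere.** Week 24 results are also planned for ICU admission, hospital and ICU days, and all-cause death. These would temper a false impression from a flat ventilation curve.

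**Few events are likely.** Protocol 2.2.1 reports 8 of 1039 treated patients (0.77%) hospitalized through Day 28 in a broader high-risk trial. Applied to 150 participants, that is 150 × 0.0077, or about 1.2 admissions. Risk in immunocompromised patients over 24 weeks may well be higher, so this bounds nothing, but it suggests small counts.

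The general statement in Protocol 4.1 that efficacy assessments run through Week 24 does not help the plan, because the specific row for oxygen support is blank at those visits.

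**Conclusion.** The point holds in this form. SAP 6.2.13 and Appendix 1 give different follow-up limits for ventilation or ECMO, and only the Day 44 limit matches the scheduled data. If 6.2.13 is followed, about 124 of 168 days (112 to 135 with windows) have no scheduled capture for event-free participants. The Week 24 proportion would then essentially repeat the Day 44 proportion and could understate late events by an amount that cannot be estimated from the documents.

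A reader might also infer that these days count as event-free for every participant. They do not: anyone with an event by Day 44 has already been counted. Nor does the protocol single out respiratory failure after Day 44 as a concern; its rationale speaks of progression to severe illness in prolonged infection.

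The conclusion assumes that the CRF has no ventilation field on the medical-visit page at Weeks 12 and 24. The event counts and losses in the illustrations are assumptions. The endpoint is one of many secondary ones, all analyses are descriptive, and the primary result is unaffected. The correction is still worth making, because it is cheap and the Week 24 figure would claim observation that the schedule does not provide.

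**What to change.** **Preferred.** Delete the Week 24 horizon from SAP 6.2.13 and censor event-free participants at the earlier of Day 44 and their last oxygen-support assessment. This agrees with Appendix 1 and the schedule, and removes the later-of rule for this endpoint. It is a one-line SAP edit that needs no new data and can be made even if the long-term visits have passed. The cost is that no Week 24 figure is reported for this endpoint; no protocol commitment is lost, since the protocol states no horizon.

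**Alternative, only if the Week 12 and Week 24 visits are still ahead.** Mark the oxygen-support row at both visits, asked alongside the medical-visit question already scheduled there. Amend the Appendix 1 cap to match, and censor at the last date on which oxygen support was assessed. The cost is one CRF item at two existing visits plus a change to the protocol schedule. If the CRF already records ventilation at those visits, stating so in Protocol 8.2.2 or 8.2.3 and aligning Appendix 1 and the censoring rule would be enough.

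Either way, reconcile the Appendix 1 rows for hospitalization and ICU admission with SAP 6.2.11 and 6.2.12 in the same revision.
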